5.2.2 Plasma infusion day

Patients randomized to the treatment arm will need to be seen on the day of infusion which should occur within 48 hours of randomization and be within 96 hours of symptom onset.

Study plasma administration will be allowed for the Control arm after hospital admission if requested by the patient's medical team.

- On the day of infusion, blood will be drawn for:
 1. Inflammatory markers

- a. D-Dimers
 - b. Ferritin
 - c. CRP
- 2. Serological testing: anti-SARS CoV-2 titers
- 3. Exploratory blood test for genomics (optional)
- 4. Exploratory blood test for cytokines/chemokines (optional)
- 5. Rectal swab for gut microbiome analyses, to be sent to the CDI if possible
- 6. CBC
- 7. Complete chemistry
- 8. ABO Rh

- Procedure:
 - 1. A single unit of approximately 400-500 mL of liquid fresh plasma or 2 units of fresh frozen plasma for a total of approximately 400 mL will be transfused at an approximate rate of 50 mL per hour x 30 minutes, then the rate may be increased up to 150 mL per hour until completion. If plasma availability does not allow for 2 units of FFP, a single unit may be administered.
 - 2. If possible, 10mL of plasma will be collected for research from the infusion line and sent to the CDI
 - 3. The infusion may be slowed or stopped as per investigator's decision for minor transfusion reactions only. The transfusion will be discontinued for any transfusion reactions other than minor allergic reactions.
 - 4. An investigation will be initiated when there are signs of a systemic transfusion reaction.
 - 5. Premedication 30 – 60 minutes prior to the infusion will include 100 mg hydrocortisone IV and may include acetaminophen 650 mg PO and diphenhydramine 25 mg IV. Diphenhydramine 25 mg IV and hydrocortisone 100 mg IV may be repeated as needed for an infusion reaction at the discretion of the investigator.
 - 6. Vitals signs should be monitored following Hackensack Meridian Health Blood and Blood Product Administration SOP guidelines:
 - a. Temperature, pulse, respirations, and blood pressure pre-infusion (within 30 minutes), 15 minutes after the start, every hour during, if a transfusion reaction is suspected or if there is any change in patient condition, post transfusion (5-15 minutes post)

5.2.3 Post enrollment day +3 and day +7 (or closest working day). May be done remotely.

- COVID-19 symptom screen by telephone (Y/N)
 - 1. Fever (T max)
 - 2. Cough
 - 3. Shortness of breath
 - 4. Ageusia and/or anosmia

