 - 5. Myalgias
 - 6. Headaches
 - 7. Other symptoms that the patient attributes to their COVID-19 infection

- New medical conditions, AE evaluation
- Safety assessment
- Rectal swab for microbiome at day +3 and day +7 to be sent to the CDI if possible.

5.2.4 Post enrollment: 2 weeks (+/- 3 days), 4 weeks and 2 months (+/- 5 days). Preferably in person.

- COVID-19 symptom screen (Y/N)
 1. Fever (T max)
 2. Cough
 3. Shortness of breath
 4. Ageusia and/or anosmia
 5. Myalgias
 6. Headaches
 7. Other symptoms that the patient attributes to their COVID-19 infection
- New medical conditions, AE evaluation
- Safety assessment
- Serological testing: anti-SARS CoV-2 titers if possible.
- Swab for COVID-19 testing at 2 weeks, and again at 4 weeks if week 2 is positive.
- Exploratory blood test for cytokines/chemokines at +2 and +4 weeks to be sent to the CDI if possible.
- Rectal swab for microbiome at +2 weeks, +4 weeks, and +2 months to be sent to the CDI if possible.

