8.3.3 Secondary Endpoints

- Time to Symptoms Resolution

Kaplan-Meier analysis will be used to describe time to symptoms resolution and the median time with 95% CI will be reported. Log-rank test will be utilized to compare the time to symptoms resolution between the Treatment and Control arms.

The time to symptoms resolution is defined as the time in days from therapies initiation to the first documented symptoms resolution as assessed by a local site. Patients whose symptoms are not resolved, or result in death, or lost follow-up on the designed follow-up date, will be censored on that date.

- Overall Survival (OS)

Overall survival (OS) will be defined as the time in days from study entry to death. Patients who are alive on the date of closing follow-up will be censored on that date. All events of death will be included, regardless of whether the event occurred while the subject was still taking new therapies, or after the subject discontinued study therapy. If a subject has not died, then the data will be censored according to the following rule: if the subject was lost to follow-up, then data will be censored at the last study visit, or the last contact date, or the date the subject was last known to be alive, whichever is later. If the subject was not lost to follow-up, then data will be censored at the last study visit or the last contact date, whichever is later.

OS will be estimated by Kaplan-Meier methodology, and median OS with 95% CI will be reported. And the OS between the Treatment and Control arms will be compared by Log-rank test.

- Rate of Virologic Clearance

The rate of virologic clearance by nasopharyngeal swab at 2 weeks and 4 weeks will be summarized by frequency (%) and compared between two randomized arms by Mantel-Haenszel test. The marginal model will be fitted to the rate of virologic clearance at different time points to evaluate the main effect of randomized arms by using the generalized estimating equations method.

Viral clearance at a designed follow-up date is defined as the cycle threshold (Ct) of RT-PCT at that designed follow-up date 40.

- Evaluation of Donor parameters

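### Time to symptom resolution is analysed as if exactly dated, but the only listed source is a yes/no screen at five contacts, so medians would run late and the log-rank test would lose power

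*Combined protocol and SAP*

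**What the plan says.** Section 8.3.3 runs the event time from the start of therapy to the "first documented symptoms resolution as assessed by a local site". For the Kaplan-Meier estimate, "the median time with 95% CI will be reported". For the comparison, "Log-rank test will be utilized to compare the time to symptoms resolution between the Treatment and Control arms". No interval-censored method is named.

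Symptoms are collected at five contacts after baseline:

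- Section 5.2.3: "Post enrollment day +3 and day +7 (or closest working day). May be done remotely". The item is a telephone symptom screen answered yes or no, with maximum temperature for fever.
- Section 5.2.4: "Post enrollment: 2 weeks (+/- 3 days), 4 weeks and 2 months (+/- 5 days). Preferably in person". The item is again "COVID-19 symptom screen (Y/N").

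Neither section lists a diary or a date on which symptoms ended. The adverse event form takes end dates, but Section 7.1.2 directs to it events that start or worsen after donation or infusion. A presenting COVID-19 symptom that simply clears is not such an event.

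**The concern.** A patient who recovers on day 15 is first seen to be well at about day 28. Ordinary Kaplan-Meier treats day 28 as the exact day of recovery. The gaps between scheduled contacts are 3, 4, 7, 14 and 32 days, so the error grows with time.

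Three results are at stake. The reported median may describe the visit calendar more than the illness. Its confidence interval reflects sampling error only and does not cover this shift. The log-rank test works on coarsened times and may miss a real difference more often. This is the first secondary objective listed in Section 2.2, and a date that nobody asks for during follow-up is hard to recover later.

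**Working it through.** **Inputs from the documents.** Contacts at days 3, 7, 14, 28 and 60, with windows of 3 days at week 2 and 5 days at month 2 (5.2.4); week 4 is taken as 3 days, as in Section 2.2. Final size 153 per arm (8.2). Significance at p < 0.05 (8.3.4), taken as two-sided.

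**Assumptions, not in the documents.** Weibull resolution times, various true medians, no dropout, and a window of 1 day at the telephone contacts where contacts are spread.

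**The plan's own figures.** No median, hazard ratio or power is stated for this endpoint. The primary design does reproduce: simulating the stated boundaries gives a type I error of 0.0498 with binding futility, and power of 0.802 to 0.806 for 8% versus 18%. So 153 per arm is a fair basis for a fully enrolled trial.

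**Step 1: one case by hand.** Take true medians of 9 and 12 days, Weibull shape 1.3, contacts exactly on schedule. The proportion resolved by day d is F(d) = 1 − 0.5^((d/median)^1.3).

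- Median 9: F(7) = 1 − 0.5^0.721 = 0.393 and F(14) = 1 − 0.5^1.776 = 0.708. The recorded curve crosses one half at day 14.
- Median 12: F(7) = 1 − 0.5^0.496 = 0.291 and F(14) = 1 − 0.5^1.222 = 0.571. It also crosses at day 14.

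With 153 patients, the second arm reaches one half by day 14 with probability 0.962 and otherwise at day 28. Its average recorded median is 0.962 × 14 + 0.038 × 28 = 14.5. The first arm crosses at day 7 with probability 0.004, so its average is 0.996 × 14 + 0.004 × 7 = 14.0. A true gap of 3 days is recorded as about 0.5.

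**Step 2: visit windows added.** Simulated trials, 153 per arm, shape 1.3. Ranges are across independent runs.

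| True medians (days) | Mean recorded medians | Power, true date | Power, visit date |
|---|---|---|---|
| 8 vs 10 | 12.0 vs 14.5–14.6 | 0.69–0.70 | 0.60–0.61 |
| 9 vs 12 | 13.5–13.6 vs 16.5–16.6 | 0.90–0.91 | 0.81–0.84 |
| 15 vs 20 | 23.5–24.0 vs 28.2 | 0.90–0.91 | 0.75–0.77 |

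**Step 3: wider range.** Shapes 1.0 and 1.5, control medians from 5 to 21 days, resolution hazard ratio 1.4, 3,000 trials per case.

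- Average excess in the median: about 1 to 10.6 days. It is small when the true median lies just before a contact (6.5 is recorded as about 8) and large when it lies just after one (18 is recorded as about 27 to 28).
- Difference in medians, exact-day contacts, shape 1.5: 10.5 versus 8.5 days (dated to the day) is reported with a gap of about 0.3, while 8.5 versus 6.9 is reported with a gap of about 5.9.
- Power with daily dating: 0.80 to 0.84. With visit dating: 0.73 to 0.80 for exact-day contacts (a loss of 3 to 9 points) and 0.64 to 0.76 with windows (a loss of 7 to 18 points).
- Hazard ratio 1.0, same time origin in both arms: rejection of 0.044 to 0.058.

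**Step 4: does an interval-censored analysis help?** A Turnbull estimate on the same visit data brought the medians back to within about 1 day of the truth.

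**The case against.** **Visit dating is inferred.** The plan does not say in so many words that the event date is the contact date. The case report form is not in the documents, and Section 10.1 allows data to be abstracted from medical records, which could supply dates between contacts. This stands: if a resolution date is already captured, the problem largely goes away. Visit dating is still the natural reading of a first documented event combined with a yes/no screen.

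**A reader might infer that a difference lying inside one visit gap cannot be seen.** The documents do not support that. Medians of 9 and 12 days both lie between days 7 and 14, yet with the windows that the protocol allows, power is still 0.81 to 0.84 and the recorded medians keep a gap of about 3 days. The contrast is blurred or distorted, not lost.

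**The size is assumption-based.** No expected time to resolution is given, so every median above is assumed. The power figures also assume full enrolment. At 8% versus 18%, simulation of the stated boundaries reaches the third stage only about 32% of the time, so power near 0.90 is not what the trial would usually have. Both points stand.

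**Part of the loss comes from the windows.** Dating events at the nominal visit day raised power from 0.753 to 0.833 for 15 versus 20 days (true date 0.887), and from 0.834 to 0.853 for 9 versus 12 (true date 0.900). This stands.

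**A recalled date may be worse than a visit date.** Section 4.1 compares plasma with best supportive care and describes no placebo. Recall over gaps of two to more than four weeks could differ by arm. This stands, and is why a recalled date should not carry the main analysis.

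**Conclusion.** The point holds, conditional on the case report form not already recording a resolution date. Followed as written, the plan would report medians about 1 to 10 days too long and differences in medians that depend partly on the visit calendar. It would also lose about 3 to 18 points of log-rank power at full enrolment. These ranges rest on assumed Weibull times, assumed medians and no dropout.

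A reader might also infer that the log-rank test is invalid or that the trial's main result is at risk. Neither follows. With a common time origin the test keeps its level, and the primary endpoint, its sample size and its stopping rules do not use this variable.

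The common origin does need to be written down. Section 8.3.3 counts from the start of therapy, which Control does not have, while Section 5.2 sets day 0 at randomization and allows infusion up to 48 hours later. That is a separate matter, but the same edit can settle it. This is a correction that should be made to a secondary endpoint.

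**What to change.** In Section 8.3.3:

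1. Treat symptom resolution as interval-censored between the last contact with symptoms and the first contact without them. Report the Turnbull median with a confidence interval and compare arms with an interval-censored log-rank test.
2. Count time from randomization (day 0, Section 5.2) in both arms.
3. Optionally, add one field at each existing contact for the date on which the last COVID-19 symptom ended, and use it in a supportive analysis.

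If the case report form already captures that date, say so in Section 8.3.3 and state which date defines the event.

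The cost is a few lines of plan text and a little more analysis work, with no extra contacts. Intervals for the median will be wider, which reflects what five contacts can show. The optional field carries recall error that could differ by arm.

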Passive antibody therapy has been used for prior virus epidemics.²⁻⁶ Reports from outbreaks of severe acute respiratory syndrome (SARS) from coronavirus (SARS-CoV-1) showed that convalescent plasma from recovered patients contains neutralizing antibodies.⁷ In the 2013 Ebola epidemic, there was a significant increase in survival (72% vs 56%) for patients receiving convalescent whole blood compared to those who did not.⁸ The proposed mechanism of action by which passive antibody therapy works, is thought to be viral neutralization but may also include antibody-dependent cellular cytotoxicity.

Convalescent plasma in hospitalized patients

We are currently accruing patients on study under IND 19824 of hospitalized patients with COVID-19 infections. With 39/55 patients accrued on this study, we have found that most patients (87%) are showing anti-SARS-CoV2 titer >1:100 by the time of plasma request as very few patients are hospitalized during their first week of symptoms. Conceptually, the use of convalescent plasma is to prevent further viral invasion pending adaptive immunity. Early viral neutralization may prevent the ensuing inflammatory and coagulation cascade.

The purpose of this trial is to intervene in the early phase of viral infection to prevent hospitalization and mortality in the high-risk population.

Study Objectives

Primary Objectives

To compare the hospitalization rate of patients with early COVID-19 infection at high-risk of admission with or without convalescent plasma infusion.

Secondary objectives

- Time to symptoms resolution
- Overall survival
- Rate of virologic clearance by nasopharyngeal swab at 2 and 4 weeks.
- Evaluation of donor parameters including nasopharyngeal swab positivity and titers levels

- Evaluation of the impact of donor titers level on efficacy
- Patients' anti-SARS-CoV2 titer assessment pre-infusion for the Treatment group, +2 weeks (+/- 3 days), +4 weeks (+/- 3 days) and +2 months (+/- 5 days). Randomization day will be designated at day 0.

Exploratory Objectives

These are to be performed at Hackensack Meridian Health Center for Discovery and Innovation

- Plasma product analysis for cytokines, mannose-binding lectin (MBL), procalcitonin (PCT), C-reactive protein (CRP), Human neutrophil lipocalin (HNL), Annexin V, Surfactant protein D (SP-D), as well as microRNAs, quantification of IgG, IgM, IgA. It may not be feasible to draw samples on every plasma bag.

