4.1 Overall study design

- This is a phase II randomized study of convalescent plasma for the treatment of non-immune individuals with COVID-19 infection at high risk of complications.

- Subjects will be considered as having completed the study after 2 months (+/- 5) days, unless consent withdrawal or death occurs first.
- Subjects will be randomized to receiving convalescent plasma or best supportive care.
- Patients randomized to best supportive care may receive plasma should they require hospitalization for progression of COVID-19 disease.
- Statistical analysis will be performed as described in the statistical section 8.
- The final analysis will be conducted once the last subject completes the 2-month visit or withdraws from the study.

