Donor parameters including nasopharyngeal swab positivity and antibody titer levels. Donor parameters will be summarized by frequency (%) for categorical parameters, and mean (SD) or median [IQR, interquartile range] for continuous parameters based on the data normality. The association between the donor parameters and the hospitalization rate will be checked by Mantel-Haenszel test for categorical donor parameters, and t-test or its non-parametric version for the continuous donor parameters. The logistic regression model will be built to evaluate the main effect of donor parameters on the hospitalization rate.

- Patients' Anti-SARS-CoV2 titer Assessment

Patients' anti-SARS-CoV2 titer will be assessed pre-infusion (for the Treatment group), +2 weeks (+/- 3 days), +4 weeks (+/- 3 days), and +2 months (+/- 5 days). The antibody titers at the designed follow-up date will be summarized by mean (SD) or median [IQR] and compared between the Treatment and Control arms by t-test or its non-parametric version based on the data normality. The mixed-effect linear model will be used to assess the association between antibody titers measures with the randomized arms.

- Baseline Characteristics

All baseline summary statistics and analyses will be based on characteristics prior to the initiation of study drug. Frequency and percentages for categorical variables and mean (SD) or median [IQR] for the continuous variables based on the normalization of the data.

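### Time to symptom resolution censors patients who die unresolved as if they were lost to follow-up, so the late Kaplan-Meier curve overstates recovery unless every such death is carried to the end of follow-up

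*Combined protocol and SAP*

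**What the plan says.** Section 8.3.3 defines the endpoint as "the time in days from therapies initiation to the first documented symptoms resolution as assessed by a local site". The censoring rule is "Patients whose symptoms are not resolved, or result in death, or lost follow-up on the designed follow-up date, will be censored on that date". The analysis is then given in two sentences: "Kaplan-Meier analysis will be used to describe time to symptoms resolution and the median time with 95% CI will be reported", and "Log-rank test will be utilized to compare the time to symptoms resolution between the Treatment and Control arms".

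The rule puts three situations together: still symptomatic, dead, and lost. The date it names is not the date of death. It is the designed follow-up date, a phrase that section 8.3.3 uses twice more, both times for scheduled assessments: "Viral clearance at a designed follow-up date is defined as the cycle threshold (Ct" for the swabs at 2 and 4 weeks, and "The antibody titers at the designed follow-up date will be summarized by mean (SD) or median [IQR" for titers at 2 weeks, 4 weeks and 2 months.

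No other section treats death as a competing event for this endpoint, counts the dead as never resolved, or plans a sensitivity analysis. Overall survival is analysed separately in the same section.

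**The concern.** Kaplan-Meier censoring assumes that a censored patient has the same later chance of the event as those still at risk. That may be reasonable for a patient who is lost. It is not for a patient who has died, whose chance of resolution is zero. When the dead leave the risk set, one minus Kaplan-Meier no longer estimates the proportion of randomized patients who recover.

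This matters for the comparison because treatment may change mortality. The Protocol Summary gives the trial's purpose as "to prevent hospitalization and mortality in the high-risk population". If plasma lowers mortality, the rule withholds part of that benefit from the recovery curve. If plasma raises mortality, the rule makes recovery on plasma look better than it was.

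**Working it through.** **Inputs.** The plan states no sample size, death rate or resolution time for this endpoint, so there is no figure of its own to reproduce. From the documents: 153 per arm at the final stage (section 8.2), assumed hospitalization of 8% and 18% (section 8.1), and follow-up of 2 months (section 4.1: "Subjects will be considered as having completed the study after 2 months (+/- 5) days, unless consent withdrawal or death occurs first"), taken here as 60 days. Death shares, death times and resolution times are assumptions.

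**Illustration A.** A share m dies unresolved, with death times uniform on days 10 to 40. Survivors resolve by a Weibull law with shape 1.3 and median 12 days, the same in both arms.

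- Scale: 12 / (ln 2)^(1/1.3) = 15.9 days.
- Survivors resolved by day 60: F(60) = 1 − exp[−(60/15.9)^1.3] = 0.996.
- Share of all patients resolved by day 60: (1 − m) × F(60). For m = 0.05: 0.95 × 0.996 ≈ 0.947, allowing for rounding of F(60).
- Kaplan-Meier with the dead removed: 1 − ∏(1 − d_j/n_j), where d_j counts resolutions and n_j those still at risk. It was simulated with 400,000 patients and agrees across runs to within about 0.001.

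| Deaths m | 1 − KM at day 60, censored at death | Resolved by day 60 | Excess |
|---|---|---|---|
| 1% | 0.996 | 0.986 | 0.010 |
| 2% | 0.996 | 0.977 | 0.019 |
| 5% | 0.995 | 0.947 | 0.048 |
| 8% | 0.994 | 0.917 | 0.077 |

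The excess is close to m throughout. With 2% deaths in one arm and 5% in the other, the real gap is 0.977 − 0.947 = 0.030. The curves show 0.996 − 0.995 = 0.001.

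**Does the exact date matter?** At 5% deaths:

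- Last scheduled visit before death: 0.996, so the excess is at least as large.
- Next scheduled visit after death: 0.973 against 0.947, about half the excess. Deaths after week 4 are then carried to day 60. The 3-point gap between arms is roughly halved.
- Day 60 for every death: 0.947, with no excess.

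**Illustration B.** Resolution is exponential with median 14 days in survivors, and deaths fall on days 7 to 28. The death shares are 30% of the assumed hospitalization rates: 0.3 × 8% = 2.4% and 0.3 × 18% = 5.4%.

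- 2.4% deaths: 94.7% with deaths censored, 92.6% resolved (+2.1 points).
- 5.4% deaths: 94.4% against 89.7% (+4.7 points).
- Gap between arms: 92.6 − 89.7 = 2.9 points in truth, 94.7 − 94.4 = 0.3 on the curves.
- With 10% of the hospitalization rates (0.8% and 1.8% deaths), the excess is 0.7 and 1.6 points.
- Here censoring at the last or the next visit changes little (94.5% and 94.1% at 5.4% deaths), because no death is carried to day 60.

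**The outputs that the plan names.** Under illustration A:

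- Median, deaths censored against dead kept at risk: 12.25 and 12.25 days at 2% deaths; 12.72 and 12.73 at 5%; 13.19 and 13.22 at 8%.
- Log-rank, 153 per arm, 2% against 5% deaths, equal resolution in survivors: mean Z about 0.49 with deaths censored and about 0.90 with the dead kept at risk. Two-sided rejection is about 8% and 14%.

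**The case against.** The strongest reply is that the plan commits to a median and a log-rank test, not to a day-60 proportion. The median moves by 0.03 day or less in illustration A. The log-rank with deaths censored is a proper test of the cause-specific hazard of resolution. At modest mortality contrasts, neither version of the test would usually reach significance. Overall survival and a count of deaths are also reported, so mortality is not hidden. All of this stands, and it limits the point to the Kaplan-Meier curve and to what the comparison is taken to mean. The survival analysis does not correct the recovery curve, and the plan does not say that its log-rank addresses only the cause-specific hazard.

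The second reply is textual. A reader might infer that the plan censors on the day of death. It does not say so. If the designed follow-up date means the 2-month date for every death, the dead stay at risk and the bias disappears. That reading is possible. It is less natural, because the section uses the phrase for each scheduled visit.

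Third, a reader might infer that the excess is always largest in the arm with more deaths. That holds at similar resolution speeds and can reverse otherwise. With 3.0% deaths and a 10-day median the day-60 excess is 2.8 points; with 3.5% deaths and a 30-day median it is 1.9.

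Finally, the death rates are assumed. Patients are enrolled without an oxygen requirement or radiographic pneumonia, and at 1% deaths the excess is only about 1 point.

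**Conclusion.** The concern holds in a limited form. Section 8.3.3 chooses to censor deaths in the same way as losses. Unless every death is carried to the end of follow-up, the late part of the curve is overstated by up to roughly the proportion who die unresolved: about 2 points at 2% deaths and about 5 points at 5%. At similar resolution speeds, a mortality difference between arms is largely removed from the recovery comparison. These sizes rest on assumed death shares, death times and resolution times, and the excess shrinks with the number of deaths.

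The documents do not support the stronger conclusion that the analysis of this endpoint is invalid. The median is practically unchanged and the log-rank keeps a valid, narrower meaning. Nor is the primary endpoint, the 306 patients or the stopping boundaries affected. This is a secondary endpoint whose rule should be corrected before outcomes are seen.

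**What to change.** Replace the censoring sentence with one that says:

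- A patient who dies without documented resolution remains in the risk set as unresolved to the end of the 2-month follow-up, on one fixed day common to all patients and no earlier than the last day on which a resolution can count.
- A patient who is alive and unresolved is censored at the last visit.
- A patient who is lost is censored at the date of loss.

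Equivalently, treat death without resolution as a competing event and report the Aalen-Johansen cumulative incidence. The two agree when nobody is lost early; with losses, the Aalen-Johansen estimate is the cleaner one. The planned log-rank can be run on the recoded data, and Gray's test is an optional alternative. Whether to stratify by Charlson group is a separate matter.

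The cost is one sentence. Deaths are already collected, and the planned software (R and SAS) can do the analysis. The one drawback is that the comparison then mixes speed of recovery with survival, so the log-rank with deaths censored can be kept as a supportive analysis, labelled as a test of the cause-specific hazard. If the 2-month date was what the sponsor intended all along, the edit only makes that explicit.

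### Patients lost before symptom resolution are censored at the scheduled visit they missed instead of the last screen they completed, which biases the curve modestly toward slower resolution and lets unequal loss distort the log-rank test

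*Combined protocol and SAP*

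**What the plan says.** Section 8.3.3 defines the endpoint as "the time in days from therapies initiation to the first documented symptoms resolution as assessed by a local site". It is summarised by Kaplan-Meier, and "Log-rank test will be utilized to compare the time to symptoms resolution between the Treatment and Control arms".

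One sentence sets the censoring for three groups together: patients whose symptoms have not resolved, patients who die, and patients lost. It ends "or lost follow-up on the designed follow-up date, will be censored on that date". The only date it names is the designed follow-up date.

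The overall-survival paragraph of the same section has a separate rule for lost patients, which takes the latest of three dates: "data will be censored at the last study visit, or the last contact date, or the date the subject was last known to be alive".

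Symptom status is recorded at scheduled contacts only. Section 5.2.3 reads "Post enrollment day +3 and day +7 (or closest working day). May be done remotely", and section 5.2.4 reads "Post enrollment: 2 weeks (+/- 3 days), 4 weeks and 2 months (+/- 5 days). Preferably in person". The plan gives no last-contact rule and no sensitivity analysis for symptom resolution.

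**The concern.** A resolution is an event only when it is documented, and documentation happens at the screens, so events cluster on visit dates. Kaplan-Meier and the log-rank test treat a patient censored on day t as still at risk for events on day t. A patient who misses the week-2 screen and is censored on the week-2 date is therefore in the denominator for the week-2 resolutions but cannot be one of them. That visit's resolution rate is diluted by the fraction lost since the previous screen.

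If both arms lose patients equally, both curves shift slightly and the comparison survives. If loss differs, the arm with more loss appears to recover more slowly. Section 4.1 states "Subjects will be randomized to receiving convalescent plasma or best supportive care" and no placebo is described, so unequal loss is possible. What is at stake is the credibility of a secondary efficacy comparison, for a rule that costs almost nothing to put right.

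**Working it through.** **Plan's own figure.** The documents give no power, median or loss rate for this endpoint, so there is nothing to reproduce.

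**Inputs from the documents.** 153 per arm (8.2); screens at days 3, 7, 14, 28 and about 60 (5.2.3, 5.2.4); log-rank test (8.3.3); p below 0.05 (8.3.4, sidedness not stated; two-sided taken, so 2.5% in the direction of plasma faster).

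**Assumptions.** Exponential resolution with a 12-day median, the same in both arms; loss unrelated to symptoms; total loss L spread evenly over the five visits.

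**Which date.** Section 8.3.3 uses *designed follow-up date* for viral clearance (swabs at 2 and 4 weeks) and for antibody titers (2 weeks, 4 weeks, 2 months). For the end of follow-up, the overall-survival paragraph speaks of closing follow-up. On that usage, the date for a lost patient is the missed visit.

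**Step 1, true resolution rate per visit.** h = 1 − 2^(−gap/12). For gaps of 3, 4, 7, 14 and 32 days, h = 0.159, 0.206, 0.333, 0.555 and 0.842.

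**Step 2, loss per visit.** q = 1 − (1 − L)^(1/5).

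- L = 5%: q = 0.0102
- L = 10%: q = 0.0209
- L = 15%: q = 0.0320
- L = 25%: q = 0.0559

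**Step 3, dilution.** With missed-visit censoring the recorded rate at each visit is h(1 − q). With no true effect, the Control-to-Treatment ratio of recorded rates is (1 − q_C)/(1 − q_T).

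- 5% vs 15%: 0.9680/0.9898 = 0.978
- 5% vs 25%: 0.9441/0.9898 = 0.954

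**Step 4, log-rank shift.** At the first visit, expected recorded resolutions are 153 × 0.1591 × 0.9898 = 24.09 (Treatment) and 153 × 0.1591 × 0.9680 = 23.56 (Control). With equal numbers at risk, observed minus expected is (24.09 − 23.56)/2 = 0.27. The number at risk is then multiplied by (1 − h)(1 − q) in each arm, and the step is repeated over the five visits with the usual tied-data variance.

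| Loss, Treatment vs Control | Sum of O − E | Variance | Mean Z | 1 − Φ(1.96 − Z) |
|---|---|---|---|---|
| 5% vs 15% | 1.54 | 41.1 | 0.24 | 4.3% |
| 5% vs 25% | 3.15 | 40.1 | 0.50 | 7.2% |
| 10% vs 10% | 0 | 41.1 | 0 | 2.5% |
| 15% vs 5% | −1.54 | 41.1 | −0.24 | 1.4% |

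**Step 5, check by simulation.** Full log-rank simulation with a 12-day median gave 4.2% and 7.3% for the first two rows. Other assumed loss timings gave 4.1-5.0% and 6.8-8.8%. Last-contact censoring gave 2.3-2.8%. With medians of 7 and 14 days, the two-sided error was 5.8-6.4% (5% vs 15%) and 7.3-8.2% (5% vs 25%), against 4.6-5.0% with censoring at the last attended visit. Equal loss of 20% left every rule at 4.3-5.4%.

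**Step 6, equal loss of 10%.** The unresolved share at day 28 is 2^(−28/12) = 19.8%. Under missed-visit censoring it is the product of 1 − h(1 − 0.0209) over the first four visits, which is 20.8%. Simulated power at hazard ratio 1.4 moved from 0.79 to 0.78, or from 0.77 to 0.76, depending on when loss occurs.

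**Worst-case reading.** If the date meant the 2-month visit, 5% vs 15% loss gives about 9-22% across most of the loss timings tried; the most extreme gave 31%.

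**The case against.** The best defence is that the sentence is clumsy and was not meant as a deliberate rule. It can be read as censoring each group on its own relevant date, and the sponsor may have intended last contact. That is possible, but the words do not say it, and a programmer following them would use the scheduled date. The same edit is needed either way.

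It is also fair to say that two different endpoints may have different censoring rules. The overall-survival rule does not contradict this one. It shows only that a last-contact rule was available and was not applied here.

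A reader might infer two stronger things.

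- **The distortion is large, because lost patients stay at risk to month 2.** The section's wording does not support this, since it uses the phrase for individual visits.
- **The rule manufactures a benefit for plasma.** This needs higher loss in Control. The documents give no loss rates, and after the infusion visit both arms have the same contacts. If Treatment lost more, the rule would work against plasma, as the last row of the table shows.

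What stands of the defence is that the effect is small on the supported reading, and that inflation needs a sizeable imbalance. At 5% versus 10% loss, the false rate is only 3.3-3.4%.

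**Conclusion.** The point holds as a modest bias in a secondary endpoint. Followed literally, section 8.3.3 keeps unobserved patients in the risk set at visits where resolutions are counted. With 5% versus 15% loss, the one-sided false-positive rate rises from about 2.5% to about 4%; with 5% versus 25%, to about 7-8%. With equal loss there is no inflation, the day-28 unresolved share rises by about one percentage point at 10% loss, and power barely changes.

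The median, the loss rates, their timing and the hazard ratio are assumptions; only the visit schedule, the arm size, the test and the 0.05 level come from the plan. The 2-month figures are a worst case only. They do give a reason to settle the date before outcome data by arm are seen. The primary hospitalization comparison in 8.3.1 does not use this rule and is unaffected.

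**What to change.** In 8.3.3, replace the single censoring sentence with three clauses:

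1. Patients lost to follow-up before resolution are censored at the last completed symptom screen at which they were unresolved (day 0 if no later screen was completed).
2. Patients still symptomatic at the final visit are censored at that visit.
3. Deaths before resolution are covered by their own explicit clause, so that splitting the sentence does not leave them without a rule.

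The screens in 5.2.1, 5.2.3 and 5.2.4 already supply the dates. The change needs no new data, visits or patients. Reporting loss before resolution by arm beside the Kaplan-Meier curves would let readers judge whether any imbalance remains.
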